List of Appendices

Appendix		Page
Appendix 1.	Abbreviations and Definitions	64
Appendix 2.	Clinical Laboratory Tests	68
Appendix 3.	Study Governance Considerations	69
Appendix 4.	Hepatic Monitoring Tests for Treatment-Emergent Abnormality	73
Appendix 5.	Sampling Summary	74
Appendix 6.	Protocol Amendment I7X-MC-LLCF(c) Summary Effect of LY3202626 on Alzheimer's Disease Progression as Measured by Cerebral ¹⁸ F-AV-1451 Tau-PET in Mild Alzheimer's Disease Dement	tia75

1. Synopsis

Title of Study:

Effect of LY3202626 on Alzheimer's Disease Progression as Measured by Cerebral ¹⁸F-AV-1451 Tau-PET in Mild Alzheimer's Disease Dementia.

Rationale:

Eli Lilly and Company (Lilly) is developing LY3202626, a synthetic small molecule which is a potent inhibitor of β -site amyloid precursor protein (APP)-cleaving enzyme [BACE]1, for the treatment of Alzheimer's disease (AD). It is hypothesized that inhibition of BACE1 may slow or inhibit the progression of AD.

Study I7X-MC-LLCF (LLCF), a Phase 2 study, will assess if inhibiting the production of $A\beta$ in the brain through BACE1 inhibition with LY3202626 can slow the progression of disease as assessed by biomarkers of neurodegeneration over 52 weeks of treatment. The ¹⁸F-AV-1451 positron emission tomography (PET) scan is the primary outcome measure as a marker of disease progression for this study, to assess cerebral tau neurofibrillary tangle load and whether there are any changes with $A\beta$ targeted BACE inhibitor treatment. The study will also assess LY3202626 pharmacokinetics (PK) and pharmacodynamics (PD; plasma $A\beta$), biomarkers of amyloid pathology (florbetapir PET) and neurodegeneration (volumetric magnetic resonance imaging [vMRI] and cerebral perfusion). In addition, LY3202626, $A\beta$, and tau in cerebrospinal fluid (CSF) will be collected in a substudy to assess the PK of LY3202626, PD (CSF $A\beta$), and neurodegeneration (CSF tau) within the central nervous system (CNS). Clinical outcomes including cognition, functional consequences of cognition, and safety will also be evaluated.

Objective(s)/Endpoints:

Objectives	Endpoints
Primary To assess the change from baseline in ¹⁸ F-AV-1451 positron emission tomography (PET) after treatment with LY3202626 3 mg or 12 mg per day compared with placebo for 52 weeks among patients with mild Alzheimer's disease (AD) dementia and evidence of brain amyloid.	The change in standardized uptake value ratio (SUVr) of ¹⁸ F-AV-1451 PET from baseline to 52 weeks. The change will be compared between the LY3202626 doses (3mg and 12mg) and placebo.
Secondary • To evaluate the safety and tolerability of LY3202626 (3 mg and 12 mg per day) compared with placebo.	Standard safety assessments: spontaneously reported adverse events (AEs) clinical laboratory tests vital sign and body weight measurements 12-lead electrocardiograms (ECGs) physical and neurological examinations magnetic resonance imaging (MRI; amyloid-related imaging abnormality [ARIA] and emergent radiological findings) Skin examination Eye examination Columbia-Suicide Severity Rating Scale (C-SSRS)

Objectives	Endpoints
To assess peripheral pharmacokinetics (PK) and pharmacodynamics (PD) of LY3202626 (3 mg and 12 mg per day) over 52 weeks.	 Plasma PK of LY3202626 Plasma Pharmacodynamics Aβ₁₋₄₀, Aβ₁₋₄₂, Aβ_{1-x}
 To assess change from baseline in cognition after 52 weeks of treatment among patients treated with LY3202626 (3 mg and 12 mg per day) compared with placebo. 	13-item Alzheimer's Disease Assessment Scale – Cognitive subscale (ADAS-Cog13)
 To assess change from baseline in function after 52 weeks among patients treated with LY3202626 (3 mg and 12 mg per day) compared with placebo. 	Alzheimer's Disease Cooperative Study- instrumental Activities of Daily Living inventory (ADCS-iADL)
 To assess change from baseline in a composite measure of cognition and function after 52 weeks among patients treated with LY3202626 (3 mg and 12 mg per day) compared with placebo. 	integrated Alzheimer's Disease Rating Scale (iADRS)

Summary of Study Design:

Study I7X-MC-LLCF is a multicenter, multi-region, randomized, double-blind, placebo-controlled study in patients with mild AD dementia and demonstration of amyloid pathology by florbetapir PET tracer. The study will test the effect of two oral doses of LY3202626, a potent BACE1 inhibitor, on ¹⁸F-AV-1451 PET and evaluate the cognition, function, safety profile, PK and PD of LY3202626 in this population.

Treatment Arms and Duration:

Patients will initially be randomized into 1 of 3 treatment groups: 2 fixed dose levels of LY3202626 (3 mg and 12 mg per day) and placebo (1:1:1) until approximately 45 participants are enrolled in each arm; then randomization will change to 1:1 with subjects entering either the 12 mg or placebo arm. Treatment duration for all subjects will be 52 weeks.

Number of Patients:

Approximately 380 patients will be enrolled for approximately 320 completed evaluable patients, assuming approximately 15% drop out.

Statistical Analysis:

Patient Characteristics:

Standard baseline characteristics of gender, age, and race will be summarized for all patients. Treatment group comparisons will be made using Fisher's exact test for categorical data and an analysis of variance (ANOVA), with an independent factor for treatment for continuous data. Diagnosis, illness characteristics, and baseline efficacy and safety measures will be analyzed in a similar manner.

Efficacy:

The primary objective of this study is to assess the effect on neuropathological progression of 2 different LY3202626 doses in patients with mild AD dementia compared with placebo, measured by change in ¹⁸F-AV-1451 PET standardized uptake value ratio (SUVr) at baseline and week 52. The primary measurement is change from

baseline ¹⁸F-AV-1451 PET SUVr at Week 52. An analysis of covariance (ANCOVA) will be used to statistically evaluate change in ¹⁸F-AV-1451 PET from baseline at 52 weeks post-dose.

Statistical analyses of mean change in efficacy and health outcome measures will be conducted. Generally, statistical assessment of the efficacy and health outcome measures will be a mixed model repeated measure (MMRM) or an ANCOVA. The primary comparison will be between LY3202626 12 mg versus placebo at endpoint.

Safety:

Safety will be assessed by summarizing and analyzing adverse events (AEs), laboratory analytes, vital signs, electrocardiograms (ECGs), skin examinations, and eye examinations during the treatment period. For continuous safety measurements, a change from baseline will be analyzed using MMRM or ANCOVA model. Safety analyses for the treatment period will include comparisons between LY3202626 dose groups and placebo. All hypotheses will be tested at a 2-sided 0.05 significance level. No adjustments for multiple comparisons will be made.

For analysis comparing proportion of treatment-emergent abnormalities between treatment groups for laboratory analytes, vital signs, weight, ECGs, skin examinations, and eye examinations, only patients who have both a baseline observation and a postbaseline observation will be included in the analysis for each analyte or parameter, respectively. The proportion of patients with abnormalities will be summarized and compared between treatment groups using Fisher's exact test.

Pharmacokinetics/Pharmacodynamics:

Plasma LY3202626 concentration data will be analyzed using a population approach. For each dose level and visit, plasma $A\beta_{1-40}$, $A\beta_{1-42}$ and $A\beta_{1-x}$ concentrations will be summarized and mean change from baseline will be calculated. If appropriate, a modeling approach may be used to describe the change in plasma $A\beta$. Additional exploratory analyses of the data will be conducted as suggested by the data. If appropriate, the data from this study may be combined with that from other studies in a meta-analysis.

Interim Analysis:

An interim analysis is planned for when data from approximately 105 qualified patients at 12 weeks (Study Visit 8) and 75 patients through 24 weeks (Study Visit 11) have been obtained. The interim analysis will be conducted for safety, and to support initial PK model development. An early lock of the PK/PD dataset will be conducted after all patients complete 24 weeks of treatment to prepare for final PK/PD model development.

2. Schedule of Activities

Study Procedure		reening Period	Double Rlind Period																	
Visit ^a	V1 ^b	V2	V3	V4	V5	V6	V7	V8	V9	V10	V11	V12	V13	V14	V15	V16	V17	V18	Follow Up	EDc
Week	-6	0 to -1 ^d	0	1	2	4	8	12	16	20	24	28	32	36	40	44	48	52	56	
Tolerance Interval (days)				±5	±5	±7	±7	±7	±7	±7	±7	±7	±7	±7	±7	±7	±7	±10	±10	
Administrative																				
Subject Informed Consent	X																			
Subject number assigned	X																			
Study Partner Informed Consent ^v	X																			
Randomization			X																	
Clinical Assessments																				
Demographics	X																			
Medical/Psychiatric History	X																			
Inclusion/Exclusion Criteria	X	X	X																	
Prior/Concomitant Medications	X	X	X	X	X	X	X	X	X	X	X	X	X	X	X	X	X	X	X	X
Habits	X																			
NIA-AA criteria review	X																			
Efficacy and Health Outcome Measures ^e																				
MoCA ^f	X										X							X		X
ADAS-Cog ₁₃			X								X							X		X
ADCS-ADL			X								X							X		X
FAQ			X								X							X		X
MMSE ^f	X										X							X		X
ECog			X								X							X		X
NPI			X															X		X
BASQID			X															X		X
Imaging Measures ^{c,g}																				
MRI	X																	X		X
Florbetapir PET (including perfusion)	X																	X		X
¹⁸ F-AV-1451 PET		X																X^h		X^h
Laboratory Measures																				
Urinalysis	X		X					X			X			X				X		X
Blood sample for APOE genotyping		X																		
Blood sample for pharmacogenetics		X																		

Study Procedure		reening Period									Do	uble E	Blind	Perio	1					
Visit ^a	V1 ^b	V2	V3	V4	V5	V6	V7	V8	V9	V10	V11	V12	V13	V14	V15	V16	V17	V18	Follow Up	ED ^c
Week	-6	0 to -1 ^d	0	1	2	4	8	12	16	20	24	28	32	36	40	44	48	52	56	,
Tolerance Interval (days)				±5	±5	±7	±7	±7	±7	±7	±7	±7	±7	±7	±7	±7	±7	±10	±10	
Blood sample for epigenetics		X																X		
Blood sample for RNA ⁱ		X																X		
Plasma LY3202626 (PK) ^j					X^k	X^k	X^{l}	X^k	X^{l}		X^{m}									X
Plasma peptides: $A\beta_{1-40}$, $A\beta_{1-42}$, $A\beta_{1-x}$ (PD) ⁿ		X			X	X	X	X	X		X							X		X
Plasma samples (EDTA) for storage and exploratory biomarker R&D		X				X	X	X	X	X	X			X				X		X
Clinical Chemistry, Hematology, Electrolytes ^o	X		X		X	X	X	X	X	X	X			X				X	X	X
Safety Measures																				
Eye Examination ^p	X							X					X					X		X
Skin Examination ^q	X							X			X							X		X
Physical/Neurological Examination	X		X		X		X			X				X				X		X
Vital Signs ^r	X	X	X	X	X	X	X	X	X	X	X	X	X	X	X	X	X	X	X	X
Height	X																			
Body weight	X							X			X							X		X
12-lead ECG(triplicate)	Xs		X	X		X	X		X		X		X		X			X	X	X
C-SSRS ^t /Self Harm Supplement Form	X	X	X	X	X	X	X	X	X	X	X	X	X	X	X	X	X	X	X	X
Dispense Drug			X^{u}			X	X	X	X	X	X	X	X	X	X	X	X			
Assess Drug Compliance				X	X	X	X	X	X	X	X	X	X	X	X	X	X	X		X
Adverse Events		X	X	X	X	X	X	X	X	X	X	X	X	X	X	X	X	X	X	X

Abbreviations: Aβ = amyloid beta peptide; ADAS-Cog₁₃ = 13-item Alzheimer's Disease Assessment Scale – Cognitive subscale; ADCS-ADL = Alzheimer's Disease Cooperative Study-Activities of Daily Living inventory; APOE = apolipoprotein E; BASQID = Bath Assessment of Subjective Quality of Life in Dementia; C-SSRS = Columbia-Suicide Severity Rating Scale; ECG = electrocardiogram; ECog = Everyday Cognition; ED = early discontinuation; EDTA = ethylenediaminetetraacetic acid; FAQ = Functional Activities Questionnaire; MMSE = Mini-Mental Status Examination; MoCA = Montreal Cognitive Assessment; MRI = magnetic resonance imaging; NIA-AA = National Institute on Aging-Alzheimer's Association; NPI = Neuropsychiatric Inventory; PD = pharmacodynamics; PET = positron emission tomography; PK = pharmacokinetics; R&D = research and development; RNA = ribonucleic acid; V = visit.

^a Every effort should be made for visits to occur on the designated study days. The overall treatment period in the protocol should be maintained (that is, visits should be scheduled based on the baseline visit rather than the previous visit). Study procedures designated for a specific visit should be performed within 1 day whenever possible. If the time spent at the site needs to be minimized, the assessments can be completed over a longer period.

- b Visit 1 takes place over more than 1 day. Clinical scales should be administered before imaging procedures are conducted.
- Only capture imaging measures (MRI, florbetapir F 18 PET, and ¹⁸F-AV-1451 PET) at the ED visit if at least 24 weeks have passed since the baseline measurement was obtained. Note: Patients should be encouraged to remain in the study after their ED Visit until Week 52 (Visit 18), even if study treatment has been discontinued. Patients who discontinue treatment, but remain in the study should continue to participate in all scheduled visits and assessments, as appropriate, with the exception of PK measurements and PET scans. The follow-up visit (Week 56) is not required for patients who discontinue study treatment early and continue in the study, unless the study drug was discontinued within that last 4 weeks of the study.
- d Screening period exceeding 60 days will not be considered a protocol deviation. If the screening period exceeds 120 days, sites should contact the Lilly-designated medical monitor for guidance.
- ^e If clinical scales are administered on the same day as medical procedures that could be stressful for the patient (for example, blood draws and imaging), the clinical scales should be administered first.
- The MoCA and the MMSE should not be administered in succession (that is, at least one other scale should be administered between them) and should be done by different raters.
- The baseline ¹⁸F-AV-1451 scan should not be performed until a positive florbetapir F 18 PET result has been confirmed by central read and all other screening criteria have been confirmed. Florbetapir F 18 and ¹⁸F-AV-1451 scans must be at least 16 hours apart.
- Before the Week 52 or ED ¹⁸F-AV-1451 scan, the investigator should review the patient's medical history to verify there is no risk factor for Torsades de Pointes and review the most recent ECG. If clinically meaningful abnormalities are noted on the ECG, the advisability of the ¹⁸F-AV-1451 scan should be considered by the investigator in consultation with the Lilly-designated medical monitor. Patients permanently discontinued from study treatment due to initiation of a prohibited medication known to prolong the QT-interval should not have an ED ¹⁸F-AV-1451 scan unless the scan can be performed prior to initiation of the prohibited medication.
- ⁱ Collect blood sample for RNA using PAXgene tube.
- Pharmacokinetic samples do not need to be collected for patients who discontinue study drug, but remain in the study for follow-up.
- At Visits 5, 6, and 8, patients are to hold their morning dose prior to the visit. After arriving at the site, a blood sample will be collected for LY3202626, and patients will receive their assigned dose of study drug. Prior to departing the site, a second blood sample will be collected for PK.
- At Visit 7 and 9, patients will take their morning dose at their usual time. After arriving at the site, a blood sample will be collected for PK. Prior to the patient departing the site, a second blood sample will be collected for PK.
- ^m At Visit 11, patients will take their morning dose at their usual time. A single blood sample will be collected for PK after all cognitive testing has been completed.
- One blood sample for PD is to be taken at the same times as samples for PK. If multiple PK samples are taken at a visit, the PD sample is to be taken with the first PK sample. At Visit 18 the PD sample will be taken at the same time as the other clinical laboratory samples.
- ^o See Appendix 2 for analytes to be collected by Visit.
- Eye examinations should be conducted under the supervision of an optometrist or ophthalmologist. Additional details are provided in Section 9.4.5.2.
- ^q Skin examinations should be conducted by a dermatologist. Additional details are provided in Section 9.4.5.3.
- Vital signs to be collected are blood pressure, heart rate, and temperature.
- s All ECGs are to be conducted in triplicate.

- The Baseline/Screen form of the C-SSRS will be administered at Visit 1. All subsequent measures will use the Since Last Visit form. The Self-Harm Supplement form is completed after each C-SSRS administration to enter the number of discrete events of suicidal behavior identified. If, based on administration of the C-SSRS, it is determined that suicide-related behaviors have occurred, then the Self-Harm Follow-Up (SHFU) form will be used to collect additional information to allow for a more complete assessment of these behaviors.
- Patients should be instructed to take the first dose of study drug in the morning on the day after dispensing of drug at Visit 3. For patients participating in the lumbar puncture addendum, Visit 3 LP must be performed before the first dose of study drug is administered and no later than the day after randomization.
- If the study partner changes at any time during the study, the new study partner must sign the study partner informed consent.

3. Introduction

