5.1. Overall Design

Study LLCF is a multicenter, randomized, double-blind, placebo-controlled study in patients with mild AD dementia. This study (Study LLCF) will enroll patients with mild AD dementia using National Institute on Aging-Alzheimer's Association (NIA-AA) work group consensus guidelines (McKhann et al. 2011) with amyloid deposition confirmed by florbetapir F 18 PET imaging. The treatment phase will be 52 weeks.

Figure LLCF.1 illustrates the study design.

Abbreviations: AD = Alzheimer's disease; FP = follow-up period; LY = LY3202626.

Note: This is a multicenter, randomized, parallel-group, 52-week-long double-blind, placebo-controlled, study of 2 fixed dose levels of LY3202626 (3 mg and 12 mg) in patients with mild AD dementia and evidence of amyloid pathology.

Approximately 380 mild AD dementia patients will be enrolled (approximately 167 in the placebo and 12 mg groups, and approximately 45 in the 3 mg group).

Figure LLCF.1. Illustration of study design for Clinical Protocol I7X-MC-LLCF.

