### 3. Revision History

Statistical Analysis Plan (SAP) Version 1 was approved prior to unblinding.

Statistical Analysis Plan (SAP) Version 2 was approved prior to final database lock. Due to early termination of the study, certain analyses were removed or simplified, while others were clarified. The changes in SAP version 2 are summarized below:

- Clarified that change from baseline to last observation is to be used in ANCOVA analysis if Week 52 observation is not available (Section [5.1](#))
- Removed the exploratory analysis on subjects with study partner change during the study (previously Section 5.11 in Version 1)
- Clarified the analysis for changes from baseline in NPI total score and BASQID total score will be ANCOVA instead of MMRM because they were collected only once during post-baseline visits (Section [5.11.2](#))
- Specified the cut-off for defining Tau subgroups and removed the subgroup analysis regarding race and country (Section [5.11.3](#))
- Removed sensitivity analysis on Tau PET using percentage changes from baseline (previously Section 5.12.4 in Version 1)
- Simplified analysis of CSF biomarkers to listing of values by visit by treatment due to very limited number of subjects participated in the CSF addendum (Section [5.12.2](#))
- Added analysis on annualized change in imaging biomarkers (vMRI, AV-45 PET, AV-1451 PET) because majority of the subjects would not have Week 52 observation due to early termination of the study (Section [5.12.5](#))
- Added an incidence summary for treatment-emergent CSSRS findings (Section [5.13.8.1](#))
- Simplified and clarified the analysis for categorical eye exam and eye imaging data (Section [5.13.8.3](#))

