## 5. A Priori Statistical Methods

### 5.1. General Considerations

All tests of treatment effects of biological efficacy or clinical efficacy will be conducted at a 1-sided  $\alpha=.10$ , unless otherwise stated. Safety assessments will be conducted at a 2-sided  $\alpha=.05$ .

A repeated measures analysis refers to a restricted maximum likelihood (REML)-based, mixed effects repeated measures analysis using all the longitudinal observations at each post-baseline visit.

All analyses will follow the intent-to-treat (ITT) principle unless otherwise specified. An ITT analysis is an analysis of data by the groups to which subjects are assigned by random allocation, even if the subject does not take the assigned treatment, does not receive the correct treatment, or otherwise does not follow the protocol.

When change from baseline is assessed, subjects will be included in the analysis only if both a baseline and a postbaseline measure are available. Unless otherwise defined, Visit 3 is the baseline visit, and baseline value is defined as last value available before or at Visit 3.

All total and subscale scores will be derived from individual items. If any individual item is missing, the corresponding total and subscale scores will be considered missing, except for the ADAS-Cog13 and ADCS-iADL, which will be imputed.

A repeated measures analysis model will include the fixed, categorical effects of treatment, visit, and treatment-by-visit interaction, as well as the continuous, fixed covariates of baseline, baseline-by-visit interaction, and age at baseline.

When an analysis of covariance (ANCOVA) model is used to analyze a continuous efficacy variable, the model will contain the main effects of treatment with baseline value and age at baseline added as covariates. For ANCOVA analysis on change from baseline to Week 52 endpoint, change from baseline to last observation during treatment period will be used if patients do not have Week 52 observation available.

Categorical comparisons between treatment groups will be performed using Fisher's exact tests or logistic regression where appropriate.

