### **5.6. Population for Analysis**

The Efficacy population is defined as all randomized participants who take at least 1 dose of double-blind study treatment and have at least 1 postdose efficacy measurement, which is used to assess the effectiveness of the study drug regimen; all observed data will be included (including data gathered after a subject discontinues study drug).

In order to assess the study drug treatment effect, data gathered after a subject discontinues study drug will not be included in the analysis of per protocol population.

Additionally, when change from baseline is assessed, subjects will be included in the analysis only if both a baseline and at least 1 valid post-baseline measure are available.

All subjects who received at least 1 dose of randomized study treatment (LY3202626 or placebo) will be included in the safety analysis set. If an LY3202626 dose group is dropped following an interim analysis, subjects switched to the remaining LY3202626 dose and remaining on treatment will be accounted for as a separate group.

For the Lumbar Puncture addendum, the analysis sets will include all those subjects whose eligibility was determined by the respective biomarker, who signed consent for addendum, and who have a baseline and at least 1 valid post-baseline cerebrospinal fluid (CSF) assessment.

The PK analysis set is defined as all subjects in the safety population who have at least 1 post-dose PK assessment. The population PK analyses will be performed using this analysis set.

The primary and secondary efficacy measures will be analyzed using the efficacy population unless otherwise specified. In addition, the primary measure will be analyzed using per-protocol populations to verify the robustness of the results. Summaries and analyses for safety measures will be based on the safety population.

[Table LLCF.SAP.1](#) below defines each of the analysis populations used in this study.

[Table LLCF.SAP.2](#) lists the study measures that will be summarized and/or analyzed for each population.

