**Table LLCF.SAP.1. Analysis Populations for Study I7X-MC-LLCF**

Population Name	Description of Population
Enrolled	All participants who have been assigned to treatment (randomized).
Efficacy	All randomized participants who take at least 1 dose of double-blind study treatment and have at least 1 postdose efficacy measurement.
Safety	All randomized participants who take at least 1 dose of double-blind study treatment.
Per-Protocol	All subjects in the Full Efficacy population who also: 
 
• had an assessment of the primary endpoint at each scheduled visit completed
 
• had no violations of inclusion/exclusion criteria
 
• had no study dosing algorithm violation (such as if subjects randomized to treatment A were given treatment B or subjects randomized to treatment A never received the assigned study drug)
 
• had no unqualified raters and no raters with substantial scoring errors for the primary measure
 
• was not considered non-compliant with regard to study drug
 

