## **5.11. Efficacy Analyses**

### **5.11.1. Primary Outcome and Methodology**

The primary objective of this study is to assess the PD effect of 2 different LY3202626 doses (3 mg and 12 mg) in patients with mild AD dementia compared with placebo, measured by change from baseline in 18F-AV-1451 PET SUVrs at Week 52.

The primary statistical analysis is the ANCOVA, which will be used to statistically evaluate change in composite SUVr from baseline at 52 weeks post-dose. The ANCOVA will include the fixed, categorical effects of treatment dose, and the continuous, fixed covariate of baseline Tau PET SUVr and age at baseline.

Change from baseline analyses will be conducted on SUVrs computed from the following 3 composite regions with the bimodal white matter serving as the reference region: MUBADA (primary), Delta\_Z, and the frontal lobe region defined as a weighted average (weights being the number of voxels in the region) of SUV counts, averaged bilaterally, in the following Region of Interests (ROIs):

- cingulum anterior
- Inferior frontal gyrus, opercular part
- Inferior frontal gyrus, orbital part
- Inferior frontal gyrus, triangular part
- Middle frontal gyrus
- Middle frontal gyrus, orbital part
- Superior frontal gyrus
- Superior frontal gyrus, medial
- Superior frontal gyrus, orbital part

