### **5.11.2. Key Secondary and Exploratory Outcomes**

The additional clinical and outcome measurements listed below will be analyzed separately using a mixed-effect model for repeated measures (MMRM) analysis.

The change from baseline score at each scheduled post-baseline visit (according to the Study Schedule - data collected at unscheduled visits, including early discontinuation visits if not matching the study schedule, will not be included in this analysis) during the treatment period will be the dependent variable. The model will include the fixed effects of treatment, visit

(categorical covariate), treatment-by-visit interaction, baseline age, baseline score (continuous covariate) and baseline-by-visit interaction. Visit will be considered a categorical variable with values equal to the visit numbers at which the scales were assessed. An unstructured covariance matrix will be used to model the within-subject variance-covariance errors. If the unstructured covariance structure matrix results in a lack of convergence, the following tests will be used in sequence: heterogeneous Toeplitz covariance structure, heterogeneous autoregressive covariance structure, heterogeneous compound symmetry covariance structure, and compound symmetry covariance structure. The Kenward-Roger approximation will be used to estimate the denominator degrees of freedom. Significance tests will be based on LSMeans using a 1-sided Alpha of 0.10. Analyses will be implemented using SAS PROC MIXED. Longitudinal graphs of the LSMeans estimates at each visit from the model will be plotted and the LSMeans and 95% confidence intervals (CIs) results will be summarized in a summary table.

The secondary outcomes that will be analyzed are the following:

- Change from baseline in ADAS-Cog13.
- Change from baseline in ADCS-iADL.
- Change from baseline in iADRS.

The exploratory outcomes that will be analyzed are the following:

- Change from baseline in MoCA total scores.
- Change from baseline in FAQ.
- Change from baseline in MMSE total scores.
- Change from baseline in ECog.

The following exploratory outcomes will be analyzed using the ANCOVA model described in Section 5.1:

- Change from baseline in NPI total scores.
- Change from baseline in BASQID total scores.

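### About 73% of the planned placebo group is randomised after 3 mg closes, yet the 3 mg contrast has no randomisation-period term and no concurrent-placebo analysis

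*Protocol*

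**What the plan says.** **Allocation.** The Protocol Synopsis (Treatment Arms and Duration) and Protocol 10.1.1 describe two stages. Allocation is 1:1:1 until about 45 patients are in each arm; "then randomization will change to 1:1 with subjects entering either the 12 mg or placebo arm". Protocol 5.1 gives the resulting sizes: "approximately 167 in the placebo and 12 mg groups, and approximately 45 in the 3 mg group".

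**Role of the 3 mg contrast.** SAP 4.1 compares both doses with placebo on the primary endpoint. Protocol 3.2 says the main interest in the 3 mg arm is safety and tolerability. Protocol 10.3.3.2 and 10.3.3.3 name 12 mg versus placebo as the primary comparison for the secondary and exploratory outcomes.

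**Models.** For the primary analysis, SAP 5.11.1 states: "The ANCOVA will include the fixed, categorical effects of treatment dose", with baseline SUVr and age as covariates. The MMRM in SAP 5.11.2 has treatment and visit plus "treatment-by-visit interaction, baseline age, baseline score (continuous covariate) and baseline-by-visit interaction". SAP 5.1 and 5.2 repeat these terms. Randomisation period appears in no model, subgroup (SAP 5.11.3) or analysis population (SAP 5.6, Table LLCF.SAP.1).

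**Early stop.** SAP section 3 records that the "majority of the subjects would not have Week 52 observation due to early termination of the study". For the Week 52 ANCOVAs, SAP 5.1 says that "change from baseline to last observation during treatment period will be used if patients do not have Week 52 observation available".

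**The concern.** The treatment factor has one placebo level, so all placebo patients enter the 3 mg contrast by default. Most of them are randomised after 3 mg has closed. Two things can then differ between the 3 mg and placebo groups for reasons other than the drug.

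1. **Calendar drift** in the patients recruited, the sites, scanners or raters, to the extent that baseline value and age do not absorb it.
2. **Follow-up.** With a common stop date, later entrants have equal or shorter potential follow-up. This affects the unscaled last-observation ANCOVAs (SAP 5.1, 5.13.4, 5.13.6) and the any-time or maximum safety summaries. 3 mg patients would have had longer to accumulate tau and to report adverse events.

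At stake are one of the two contrasts in the primary objective and the safety reading that is the arm's stated focus. The 12 mg contrast is 1:1 within each period and is not exposed.

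**Working it through.** **Inputs from the documents:** 45 per arm at the switch; total 380; arms 167/167/45; 1-sided alpha 0.10; dropout 15% (Synopsis) and 30% (Protocol 10.1.1 sensitivity); ED-visit PET only if at least 24 weeks after baseline (Protocol section 2). **Assumptions:** size of drift, stop dates and adverse event incidence.

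**Plan's own figure.** Placebo = 45 + (380 − 3×45)/2 = 167.5, which reproduces the stated 167.

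**Non-concurrent share.** (167 − 45)/167 = 122/167 = 73%. If half or three quarters of the later placebo patients gave no SUVr, the share would be 61/106 = 58% or 30.5/75.5 = 40%.

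**Standard errors (SD units, 15% dropout: 38.25 on 3 mg, 38.25 concurrent placebo, 141.95 placebo in all).**
- 3 mg, all placebo: √(1/38.25 + 1/141.95) = 0.182
- 3 mg, with an additive period term: √(1/38.25 + 1/(2×38.25) + 1/(2×141.95)) = 0.207, which is 13.5% larger
- 3 mg, concurrent placebo only: √(2/38.25) = 0.229, about 26% larger
- 12 mg: √(2/141.95) = 0.119 with or without the period term

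**Effect of an assumed drift D.** Bias = share × D; error = Φ(−1.2816 ± bias/SE). At 73% and D = 0.1: 0.073/0.182 = 0.40, so Φ(−0.88) = 19%.

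| Share | SE | D = 0.1 SD, favouring 3 mg | D = 0.2 SD, favouring 3 mg |
|---|---|---|---|
| 73% | 0.182 | 19% | 32% |
| 58% | 0.193 | 16% | 25% |
| 40% | 0.204 | 14% | 19% |

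If the drift runs against 3 mg, the error at 73% is 4.6% or 1.9%.

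**Per-protocol SUVr.** Table LLCF.SAP.1 requires that the subject "had an assessment of the primary endpoint at each scheduled visit completed". I read this for AV-1451 PET as baseline and Week 52. Fewer than half of 379 subjects (189.5) reach Week 52. With one stop date and 15% dropout, period 1 supplies 135×0.85 = 114.75 of these, so period 2 supplies at most 74.75, or 37.4 on placebo. The non-concurrent share is at most 37.4/(37.4 + 38.25) = 49%. At 30% dropout it is at most 47.5/(47.5 + 31.5) = 60%. The error at D = 0.1/0.2 is then at most 15/22% or 16/24%.

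**Follow-up.** Assume exponential dropout of 15% by Week 52, period 1 able to reach Week 52, and period-2 potential follow-up uniform over 20–70 or 16–60 weeks. Just under 50%, or 40%, of all subjects then reach Week 52, consistent with SAP section 3.
- Mean period-2 follow-up is 39 or 35 weeks. Mean scan time is 50.8 weeks in period 1 and 42.8 or 40.5 in period 2. The non-concurrent share of placebo scans is 71% or 69%.
- With linear change and no drug effect, the excess tau change on 3 mg is 0.714×8.0/52 = 11%, or 0.689×10.3/52 = 14%, of annual placebo change.
- Any-time adverse events (constant hazard, 3 mg versus pooled placebo): 27.8% versus 24.4% or 22.8% at 30% annual incidence (z 0.5–0.7); 56% versus 50% or 48% at 60% (z 0.7–1.0).
- Fixed follow-up of 50 weeks versus 34 to 46 weeks gives z 0.2–1.2.

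**The case against.** - **No drift is shown, and the assumed values matter.** This stands. Inverting the stated 79% power at 30% dropout (1-sided 0.10, 117 per arm) gives a working effect of about 0.27 SD, so 0.2 SD of drift would be about three quarters of it. At 0.05 SD the error is only 14%. The entry criteria and central amyloid read in the current text point to no source of drift. Equally, the plan has no analysis that would reveal one.
- **The 3 mg tau contrast carries limited weight.** Largely true: Protocol 3.2 gives the tau question to 12 mg, and the Synopsis names 12 mg versus placebo as the primary comparison for efficacy measures generally. But 3 mg remains in the primary objective.
- **The follow-up effect is inferred and conservative.** True: no enrolment or stop dates are given. It runs against 3 mg on tau and on adverse events, so it can neither create a false tau benefit nor hide harm. In the last-observation ANCOVA it would offset drift favouring 3 mg, and the error rates above do not net the two.
- **Mitigations are planned.** Annualised imaging change (SAP 5.12.5) largely removes the follow-up effect if change is linear. In addition, "the primary measure will be analyzed using per-protocol populations to verify the robustness of the results" (SAP 5.6). On the reading above this removes unequal follow-up, but it is selective and has no period term. The clinical MMRMs compare at scheduled visits. Baseline characteristics and exposure days are shown by arm. By-visit outputs exist for adverse events, laboratory values, vital signs, ECG and eye. None of these separates concurrent from later placebo, and SAP 5.13.8.2 (skin) states only any-time and maximum summaries.
- **One sensitivity analysis would be enough.** The concurrent-placebo analysis is indeed the core. The exposure-adjusted rates and skin tables suggested below are separable extras.

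**Conclusion.** The concern holds. As planned, 73% of the placebo group is non-concurrent for 3 mg, and nothing in the models or analysis populations accounts for it. The actual share after the early stop is not given and may be lower.

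The consequence is possible rather than demonstrated. An inflated false-positive rate for 3 mg needs residual drift in its favour; all the error rates above are conditional on assumed drift acting alone. The per-protocol analysis reduces exposure to drift but does not remove it. The follow-up effect alone would make 3 mg look somewhat worse on tau. The safety distortion is small and would not usually reach 2-sided 0.05. The main 12 mg comparison is unaffected. This should be fixed because the remedy is cheap.

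**What to change.** **Core change**
- Add randomisation period (before or after 3 mg closure) as a fixed effect in the ANCOVAs, including the annualised imaging ANCOVA.
- Add period and period-by-visit to the MMRMs. A main effect alone cannot absorb drift that differs between Weeks 24 and 52.
- Report 3 mg against concurrently randomised placebo as a sensitivity analysis for primary SUVr, the secondary efficacy outcomes and the main safety summaries (adverse events, treatment-emergent abnormalities, skin, eye). The additive period model assumes the 12 mg effect is the same in both periods; the concurrent-only analysis does not.
- State that the 3 mg tau result is read together with the annualised and per-protocol results.

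**Separable additions**
- Show exposure-adjusted adverse event rates beside the crude Fisher comparisons.
- For findings at scheduled examinations, rely on by-visit comparisons: already planned for eye, to be added for skin.

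**Cost.** SAP wording, one or two model terms and a small set of tables. The 12 mg standard error stays at 0.119 SD. The 3 mg standard error rises from 0.182 to 0.207 with the period term and to 0.229 with concurrent placebo only. For a safety proportion at 30% incidence, 45 versus 45 instead of 45 versus 167 raises it from √(0.21/45 + 0.21/167) = 0.077 to √(0.42/45) = 0.097, again about 26%. The concurrent-only comparison should therefore stay a sensitivity analysis.
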